**1.3 SCHEDULE OF ACTIVITIES (SOA)**

Study Day	-1	1 h	2	3	4	5 d , f	6	7	8 d , f	9	10	11 d , f	12	13	14	15 c,d,f	Daily until day 15 if discharged on study drug or daily if in hospital until day 60	22 c,d,f	29 c,d,f	60 c,d,f
Informed Consent	X b	X b																		
Inclusion/exclusion	X b	X b																		
SARS-CoV-2 Test	X b	X b																		
Pregnancy Test	X b	X b																		
Medical History	X b	X b																		
Randomization		X																		
Adverse event evaluation		X	X	X	X	X	X	X	X	X	X	X	X	X	X	X	X k	X	X	X
Vital signs a	X	x	x	x	x	x	x	x	x	x	X	x	x	x	x	x i	x i	x i	x i	x i
Physical Exam/Review of symptoms	X b	X b																		
BMI Measurement	X																			
Ordinal Score		X	X	X	X	X	X	X	X	X	X	X	X	X	X	X	X	X	X	X
SOFA Score		X		X		X			X			X				X		X	X	

Template version date 12-11-2019

*Abbreviated Title: Fostatinib for COVID*

*Version Date: 09/17/2020*

Chest x-ray	X b	X b																		
Safety labs: CBC, BMP, LFTs j	X	x		x		x			x			x				x i		x i	x i	x i
Study drug		x	x	x	x	x	x	x	x	x	x	x	x	x	x					
Research bloods		x e		x e		x e			x e			x e				x e,i		x e,i	x e,i	x e,i
Oropharyngeal swab for viral RNA		x e		x e		x e			x e			x e				x e,i		x e,i	x e,i	x e,i

- a) Vital signs include temperature, systolic blood pressure, heart rate, respiratory rate, and O2 saturation
- b) Can be done on day prior or day of enrollment, except SARS-CoV-2 test which can be done up to 7 days prior.
- c) If still in hospital phone visit not required. If discharged assess for adverse events, clinical status on ordinal scale, readmission, and mortality. Can be performed while in hospital, done as outpatient visit, or via telehealth if subject unable to travel for any reason.
- d) Can be performed +/- 2 days from scheduled visit
- e) Outpatient visit can be +/- 3 days from scheduled visit for days 5, 8, 11, 15, 22, 29, 60 as applicable

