- f) Following discharge patients only required to return for day 15, 22, 29, and 60 follow up visits unless they are discharged on study drug in which they will receive daily phone calls and will be required to have safety labs drawn as scheduled on days 3, 5, 8, 11 as applicable
- g) Day 1 is the first day of study drug
- h) Outpatient visits on day 5, 8, 11, 15, 22, 29, and 60 visits are preferred as in-person visits but may be done via telehealth and there is no need for vital signs or scheduled sample collection when telehealth is utilized unless outpatient labs can be requested via outside source (example Quest). Subjects with LFTs above 3x the ULN at enrollment will have LFTs checked daily during the hospitalization phase of the study.
- i) Outpatient adverse event monitoring will be performed via phone call
- j) Inpatient assessments will be done at the initial site of patient enrollment (NIH Clinical Center or Inova Health Systems.) After patient discharge, all outpatient assessments will be done at NIH Clinical Center, however laboratory can be done at non-NIH facility of patients who are having a telephone assessment.

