## 4 STUDY DESIGN

### 4.1 OVERALL DESIGN

We intend to study fostamatinib for the treatment of hospitalized patients with COVID-19.

- This will be a multicenter, randomized, double-blind, placebo-controlled, phase 2 trial with the objective to evaluate the safety of fostamatinib compared to matching placebo in COVID-19 patients who are hospitalized with a 5, 6, or 7 on the 8-point ordinal scale.
- The NHLBI will be the Coordinating Center for this multicenter study. All participating sites will enroll and treat subjects as described below. Research labs for exploratory endpoints will be processed at participating sites or shipped to the NIH Clinical Center for processing.
- All study participants will receive standard of care throughout the entire study and then will be randomized to 150 mg of fostamatinib twice a day or placebo for 14 days (total 28 doses).
- Subjects will be assessed daily while hospitalized and followed until day 60. If patients improve and are discharged prior to day 14 the study drug will be continued until day 14 as an outpatient. Patients who are discharged on study drug will receive a phone call daily to assess for adverse events and will have safety labs drawn on days 3, 5, 8, 11 as applicable (outpatient third party lab acquisition may be utilized as needed). We will make every effort to bring back discharged patients for outpatient visits on days 15, 22, 29, and 60 to include laboratory draws. In patients who are unable to follow-up, they will receive a telephone visit as a follow up.
- Day 1 of study is the first day of study drug and patients will be followed until day 60.

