### **Vital signs:**

Vital signs will be done daily and include temperature, systolic blood pressure, heart rate, respiratory rate, and O2 saturation.

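### Telehealth patients taking study drug at home have no secured blood-pressure reading on Days 5, 8 and 11, so the hypertension dose rules have nothing to act on

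*Combined protocol and SAP*

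**What the plan says.** Dosing does not end at discharge. Section 4.1 states: "If patients improve and are discharged prior to day 14 the study drug will be continued until day 14 as an outpatient".

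Footnote h of the Schedule of Activities (1.3) covers the outpatient visits on Days 5, 8, 11, 15, 22, 29 and 60. They "are preferred as in-person visits but may be done via telehealth", and in that case "there is no need for vital signs or scheduled sample collection when telehealth is utilized unless outpatient labs can be requested via outside source". Section 8.2 is a little stricter: phone or telehealth is for when the patient cannot be seen in person.

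For patients discharged on drug, footnote f adds daily phone calls and says they "will be required to have safety labs drawn as scheduled on days 3, 5, 8, 11 as applicable". Sections 4.1 and 8.3 repeat the calls and the labs.

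Section 6.1.2.3 sets three blood-pressure tiers: 130-139 systolic or 80-89 diastolic, at least 140 or 90, and a crisis tier above 180 or 120 mmHg. The first two start or increase antihypertensives (the first only in patients at raised cardiovascular risk). The crisis tier holds drug until pressure is below 160/100 and restarts it at 100 mg twice daily.

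On frequency, 8.3 says: "Vital signs will be done daily and include temperature, systolic blood pressure, heart rate, respiratory rate". On content, footnote a says: "Vital signs include temperature, systolic blood pressure, heart rate, respiratory rate, and O2 saturation". Neither mentions diastolic pressure.

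**The concern.** Days 5, 8 and 11 fall inside the 14-day dosing period, so for a patient discharged on drug the waiver applies while the drug is being taken. Hypertension is a labeled warning for fostamatinib (2.3.1). All patients start at 150 mg twice daily, the maximum used in immune thrombocytopenia, without the step up from 100 mg used there (4.2). Exclusion 5 removes only pressures above 160 systolic or 100 diastolic, so a patient already in the second tier of 6.1.2.3 can be enrolled, started on an antihypertensive in hospital, and sent home with no planned check on whether it is working.

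A rise in pressure often gives no symptoms, and the daily call can only act on what the patient reports. What is at stake is participant safety during home dosing and the recording of Grade 3-4 hypertension, which counts toward the secondary endpoint of Grade 3 and 4 adverse events through Day 60.

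**Working it through.** This is mainly a comparison of sections. The arithmetic only describes exposure.

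**Step 1. Is a reading secured anywhere during home dosing?**
- Footnote h: vital signs not needed at a telehealth visit; the exception concerns labs.
- Footnote f: "Following discharge patients only required to return for day 15, 22, 29, and 60 follow up visits unless they are discharged on study drug", and for those patients it then lists calls and labs only.
- 4.1: daily call and labs while on drug. The effort to bring patients back names Days 15, 22, 29 and 60, not Days 5, 8 or 11.
- 8.3, adverse events: daily call to Day 15 and labs.
- 8.3, physical examination: the targeted examination includes vital signs, but after baseline it is done only to evaluate a possible adverse event.
- 6.4: pill count at Day 15, possibly remote. No blood pressure.

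No home cuff, self-measured reading or third-party blood-pressure check appears in any of these places.

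**Step 2. The four dose-modification toxicities in 6.1.2.3, and what informs each in a telehealth patient on drug.**
- Hepatotoxicity: liver tests in the required safety labs.
- Neutropenia: blood count in the same labs.
- Diarrhea: patient report on the daily call.
- Hypertension: nothing specified.

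**Step 3. Exposure per patient.** Inputs: 14 days, 2 doses a day, 28 doses in all (4.1). The discharge day d is an assumption. Day 4 is taken as roughly the earliest, because exclusion 3 bars patients expected to leave within 72 hours. Full home-dosing days = 14 - d; home doses = 2 x (14 - d); visits open to the waiver = those of Days 5, 8 and 11 later than d.
- d = 4: 10 days, 20 doses (20/28 = 71%), 3 visits.
- d = 7: 7 days, 14 doses (14/28 = 50%), 2 visits.
- d = 10: 4 days, 8 doses (8/28 = 29%), 1 visit.

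These figures assume uninterrupted dosing and telehealth at every remaining on-drug visit.

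**Step 4. Does the Day 15 visit close the gap?** Footnote e reads: "Outpatient visit can be +/- 3 days from scheduled visit for days 5, 8, 11, 15, 22, 29, 60 as applicable". The window is therefore 15 - 3 = Day 12 to 15 + 3 = Day 18. An in-person visit on Days 12 to 14 would give an on-drug reading. The plan does not require the visit to be that early or in person, so it may help but secures nothing.

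**The case against.** The strongest reply is that attendance in person, with vital signs, is the default, and telehealth is the fallback. Footnote h prefers in-person visits and 8.2 reserves remote contact for when attendance is not possible. There are other safeguards: uncontrolled hypertension is excluded at entry, adverse events are asked about daily, a symptom leads to an examination that includes vital signs, and under 7.1 the investigator may stop drug. All of this stands, and it narrows the group at risk. None of it yields a reading in a symptom-free patient on the telehealth route.

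A reader might infer that footnote h flatly contradicts 8.3, which calls for daily vital signs, especially as the Day 2 to 14 cells of the vital-signs row carry no waiver marker. The documents do not support a firm conflict. Section 8.2 refers the reader to the schedule for follow-up assessments, and 4.1 ties daily assessment to the hospital stay, so 8.3 can be read as the general rule and footnote h as its exception. The schedule also has a separate daily column for patients discharged on drug, where vital signs carry marker i. The footnote letters appear shifted by one: Day 1 is marked h but its note is printed as g, and a marker k is used with no note k printed. Marker i therefore most likely points to the telehealth note printed as h. The mismatch in letters is not itself a design fault.

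A reader might also infer that telehealth waives the on-drug safety labs. Footnote h read alone could suggest this, but footnote f, 4.1 and 8.3 each require those labs for patients discharged on drug.

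**Conclusion.** The gap is real but narrow. It concerns patients discharged before Day 14, still on drug, and followed by telehealth. For them the plan secures no blood-pressure reading on Days 5, 8 or 11, so the hypertension rules in 6.1.2.3 cannot be applied unless symptoms prompt an examination. Per patient this covers up to 3 visits and, for the assumed discharge days, 8 to 20 of 28 doses. The conclusion does not depend on whether 8.3 and footnote h are held to conflict.

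The number of such patients is not given. It is tempting to take the 1% hypertensive-crisis rate in 2.3.1 and about 60/2 = 30 fostamatinib patients and speak of 30 x 0.01 = 0.3 expected crises. That product covers the whole arm over the whole course, including inpatient days with daily vital signs, and it carries over a rate stated without exposure time. Neither the share falling in home dosing nor the telehealth fraction is known, so no event count for this subset can be derived.

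No bias in the primary comparison of serious adverse events is shown. The point is an inexpensive improvement in safety monitoring, worth making because safety is the primary objective. The systolic-only definition in footnote a and 8.3 is a separate small mismatch, since every tier in 6.1.2.3 also has a diastolic limit.

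**What to change.** - In footnote h, limit the vital-signs waiver to visits after the last dose of study drug.
- Through Day 14, require a systolic and diastolic reading on Days 5, 8 and 11 for every patient dosing at home. It can be self-measured with a home cuff and reported on the existing daily call, or taken at the outside lab draw. Apply 6.1.2.3 to the result.
- Add diastolic pressure to footnote a and to the vital-signs paragraph of 8.3.

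The cost is protocol wording, home cuffs for some patients, and minor logistics. The daily calls and third-party lab draws are already in the plan, and neither the sample size nor the analysis changes.

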## **8.2 EFFICACY ASSESSMENTS**

For all baseline assessments and follow-up visits, refer to the Schedule of Assessments (SOA) for procedure to be done, and details below for each assessment.

Inpatient assessments will be done at the initial site of patient enrollment (NIH Clinical Center or Inova Health Systems.) After patient discharge, all outpatient assessments will be done at NIH Clinical Center either in person or remotely using NIH approved TeleMedicine software and approved NIH TeleMedicine guidance.

The subject's clinical status will be captured on each study day while hospitalized up until and including Day 60. If a subject is discharged prior to Day 15, clinical status is captured on Day 5, 8, 11, 15, 22, 29, and 60 if the subject returns for an in-person clinic visit or by phone or telehealth if an in-person visit is not possible. Clinical status will also be captured on Day 22 during a phone or telehealth visit. Clinical status is defined by secondary outcomes.

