### **8.2.2 Biospecimen Evaluations**

Research bloods will be sent from Inova hospitals to the NIH for processing in either the clinical laboratory -or- in a NHLBI research lab.

The amount of blood that may be drawn from subjects for research purposes shall not exceed 10.5 mL/kg or 550 mL, whichever is smaller, over any eight-week period.

*Abbreviated Title: Fostamatinib for COVID*

*Version Date: 09/17/2020*

Test/assay	Volume blood (approx.)	Type of tube	Frequency****	Location of specimen analysis
Routine* 
 
• CBC
 
• BMP
 
• Hepatic
 
	3 mL  4 mL	EDTA tube (lavender)  Lithium Heparin tube (light green)	Baseline (prior to enrollment)  D1-entire hospitalization, D15, D22, D29, D60 if outpatient	Clinical Lab  At participating sites
Research* 
 
• PT
 
• PTT
 
• INR
 
• Fibrinogen
 
• D-dimer
 
• Von Willebrand factor
 
	3 ml x2	Sod Citrate (BLU) x2	D1, 3, 5, 8, 11, 15, 22, 29, 60	NIH Clinical Lab
Research* 
 
• P-selectin
 
• Thrombomodulin
 
	3 ml	Sod Citrate (BLU)	D1, 3, 5, 8, 11, 15, 22, 29, 60	NIH Clinical Lab
Research* 
 
• IL-6
 
	3mL	EDTA (lavender)	D1, 3, 5, 8, 11, 15, 22, 29, 60	NIH Clinical Lab
Research* 
 
• Ferritin
 
• CRP
 
	4 mL	Lithium Heparin tube (light green)	D1, 3, 5, 8, 11, 15, 22, 29, 60	NIH Clinical Lab
Research (exploratory) 
 
• Serum tube
 
	8 mL	Serum Separator Red top tube	D1, 3, 5, 8, 11, 15, 22, 29, 60	NHLBI Research lab ([name])

*Abbreviated Title: Fostamatinib for COVID*

*Version Date: 09/17/2020*

Research (exploratory) 

• Plasma

	2 mL	Sod Citrate (BLU)	D1, 3, 5, 8, 11, 15, 22, 29, 60	NHLBI Research lab ([name])

• PBMC

	9 ml	Sodium Heparin Green top		
Research (exploratory) 

• TEG**

	3mL	Sodium Citrate	D1, 3, 5, 8, 11, 15, 22, 29, 60	NIH Site and Clinical Lab only

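### When a day 5, 8 or 11 visit is by telehealth and no outside lab can draw, one schedule note waives safety labs that three other texts require for patients still on study drug

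*Combined protocol and SAP*

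**What the plan says.** Section 4.1 continues dosing to day 14 for patients who go home early. For these patients the discharge note in section 1.3 says they "will be required to have safety labs drawn as scheduled on days 3, 5, 8, 11 as applicable". Section 4.1 gives the same days and allows a third-party lab to draw. Section 8.3 gives the same days and adds day 15. The schedule row "Safety labs: CBC, BMP, LFTs" is marked on days 3, 5, 8 and 11.

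The telehealth note in section 1.3 names outpatient days 5, 8, 11, 15, 22, 29 and 60. It prefers in-person visits but permits telehealth, and then states that "there is no need for vital signs or scheduled sample collection when telehealth is utilized unless outpatient labs can be requested via outside source". Its one condition is whether an outside lab is available; it does not mention whether the patient is still taking study drug. The last note in section 1.3 allows such draws: "however laboratory can be done at non-NIH facility of patients who are having a telephone assessment".

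Two other places bear on the point. Section 8.2 plans for remote contact on these days: after early discharge, "clinical status is captured on Day 5, 8, 11, 15, 22, 29, and 60", in person or otherwise by phone or telehealth. The routine row of the section 8.2.2 table (CBC, BMP, hepatic panel) gives its frequency after baseline as "D1-entire hospitalization, D15, D22, D29, D60 if outpatient", so it lists no outpatient draw before day 15.

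**The concern.** By the discharge note, only patients discharged on study drug have required labs between discharge and day 15. On days 5, 8 and 11 the waiver therefore falls mainly on the group that the other three texts protect.

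The draws matter because of section 6.1.2.3. Study drug stops if the neutrophil count falls below 1.0 x 10^9/L, if AST/ALT reaches three times the enrollment level, or if AST/ALT reaches 3x ULN with bilirubin above 2x ULN. Each rule acts only on a blood result. The daily call in section 8.3 asks about adverse events and cannot detect a laboratory change. The day 15 draw follows the last dose on day 14, so it cannot stop dosing.

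Section 5.2 also admits some patients with AST/ALT between 3x and 5x ULN. Section 8.3 gives those above 3x ULN at enrollment daily liver tests, but only while they are in hospital. Under the waiver such a patient could go from daily tests to none while still dosing.

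**Working it through.** The plan states no figure to reproduce. The check has two parts.

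**Texts side by side, for a patient at home on drug on day 5, 8 or 11**

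| Text | Safety labs that day? |
|---|---|
| 1.3 discharge note | Required |
| 4.1 | Required; third-party lab allowed |
| 8.3 | Required |
| 1.3 telehealth note, outside lab available | Not waived |
| 1.3 telehealth note, no outside lab | Waived |
| 8.2.2 routine row | Not listed |

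The conflict is confined to telehealth visits with no outside lab. The qualifier *as applicable* in the three requiring texts most naturally means the listed days that fall after discharge, so it does not remove the conflict. Day 3 is not in the telehealth note.

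**Size of the gap**

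Inputs:
- The last dose is on day 14 (4.1, 6.1.2.4).
- On-drug outpatient draws fall on days 5, 8 and 11.
- Assumption: a draw on the day of discharge, d, because 8.2.2 runs routine labs through the hospital stay.
- Illustrative d = 4, 6 and 9. Day 4 is near the earliest case, since section 5.2 excludes anticipated discharge within 72 hours.

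Formulas:
- Required draws left = number of {5, 8, 11} later than d.
- Gap under the waiver = 14 − d.
- Gap with all draws made = longest interval between successive draws, counting from d and ending at day 14.

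Nominal intervals:
- d = 4: 1, 3, 3, 3
- d = 6: 2, 3, 3
- d = 9: 2, 3

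Longest interval at the ±2 day extremes ("Can be performed +/- 2 days from scheduled visit"):
- d = 4: draws on 4, 6 and 13; 13 − 6 = 7
- d = 6: draws on 6 and 13; 13 − 6 = 7
- d = 9: day 11 draw taken on 9; 14 − 9 = 5

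A separate note allows ±3 days for outpatient visits. Its marker sits on the research blood and swab rows, but its wording covers outpatient visits generally. If it applies:
- d = 4: draws on 4, 5 and 14; 14 − 5 = 9
- d = 6: draws on 6 and 14; 14 − 6 = 8
- d = 9: 14 − 9 = 5

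| | d = 4 | d = 6 | d = 9 |
|---|---|---|---|
| Required on-drug draws | 3 | 2 | 1 |
| Draws under waiver, no outside lab | 0 | 0 | 0 |
| Gap to last dose under waiver (days) | 10 | 8 | 5 |
| Longest compliant gap, nominal | 3 | 3 | 3 |
| Longest compliant gap, ±2 days | 7 | 7 | 5 |
| Longest compliant gap, ±3 days | 9 | 8 | 5 |
| Excess over nominal | 7 | 5 | 2 |
| Excess over ±2 days | 3 | 1 | 0 |
| Excess over ±3 days | 1 | 0 | 0 |

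The loss of every required draw does not depend on the window. The excess length of the gap does, and in the least favorable reading it nearly vanishes.

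**The case against.** The strongest reply is that the schedule already shows what is meant. The columns for days 5, 8 and 11 carry marker f, and note f is the discharge note that requires the labs. Superscript i, which probably points to the telehealth note, appears in the safety-lab row only on days 15, 22, 29 and 60. Section 8.2 sends readers to the schedule for what to do, and three texts agree that the labs are required. A site would have to follow one note against all of these. This stands as evidence of intent, and the point is accordingly one of wording. It does not remove the conflict, because the telehealth note names days 5, 8 and 11 itself. The later marker letters also do not line up with the printed notes in the text available. That may come from PDF extraction, so it is not counted as an error, and marker placement alone cannot settle the note's scope.

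It is also fair that outside labs are provided for in 4.1 and in the last schedule note. Where one is used, the telehealth note and 4.1 agree. But those texts permit an outside draw, and none says what happens when it cannot be arranged.

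A reader might infer that telehealth patients in general go unmonitored on drug. The documents do not support that: the waiver lapses whenever an outside lab can be requested. Nor can the section 2.3.1 rates (neutropenia in 6%, AST/ALT above 3x ULN in 9%) be turned into a count of missed events, since they come without timing. Day 15 might also look like a gap, because 8.3 lists it and the discharge note does not. It is not one: the follow-up visits in 4.1, the schedule row and 8.2.2 all provide day 15 labs.

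**Conclusion.** The inconsistency is real but narrow. It arises only at a telehealth visit on day 5, 8 or 11, for a patient still on drug, with no outside lab to draw. There the telehealth note releases draws that three texts require, and 8.2.2 gives staff no prompt to obtain them. Every remaining on-drug draw (3, 2 or 1 in the examples) could be lost, and with them the only scheduled results that can trigger the neutrophil and AST/ALT stop rules before day 14.

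The gap figures assume a draw on the day of discharge, and their excess over a compliant schedule depends on which visit window governs. The documents do not say how often telehealth without an outside lab would occur, so no number of patients can be given. The likely intent is that the labs are mandatory. This is a cheap improvement to the wording, not a flaw in the monitoring design.

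**What to change.** Add one clause to the telehealth note in section 1.3: the sampling waiver does not apply to safety labs (CBC with differential, BMP, LFTs) on days 5, 8 and 11 for patients still on study drug, who have them drawn on site or at an outside lab as section 4.1 provides. If a result is missing, the investigator decides whether to hold drug. Naming the differential matters because the neutropenia rule needs the absolute neutrophil count.

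Add *D3, D5, D8, D11 if outpatient on study drug* to the routine row in section 8.2.2. No day 15 change is needed.

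The cost is wording in two places and the effort of arranging outside draws that the protocol already requires. No draws are added. The same CBCs would also supply neutrophil, lymphocyte and platelet values on those days for secondary endpoint 7.
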